## Subgroup analyses

Due to the heterogeneity of the population and a dynamic cohort in our study, we will investigate subgroup analyses to assess how the policy impact varies across different subgroups. Following the general modeling approaches as described above, we will examine the benefits of policy changes for different subgroups including (1) patients with insurance throughout the study period, (2) patients who obtained insurance after the policy changes, (3) patients without insurance throughout the study period, (4) patients newly enrolled in the system after policy changes, and (5) other subgroups of interest according to gender, age (e.g., age 65 and older), race-ethnicity. Meta-analysis has been a powerful approach to combining the effects of interest across different studies, different populations, and different subgroups. We will adopt this method to evaluate the average impact of policy changes across subgroups. A forest plot will be generated to reveal how the addition of a subgroup to the meta-analysis may affect the average policy impact.

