where  $\mathbf{x}_{mijk}$  is the vector of regressors for the fixed effects,  $\boldsymbol{\beta}_m$  is the corresponding vector of fixed-effects parameter coefficients,  $\mathbf{z}_{ij}$  is a vector of cluster-level regressors for the random effects for the  $j^{\text{th}}$  cluster of the  $i^{\text{th}}$  state,  $\boldsymbol{\gamma}_{1ij}$  is the cluster-level random-effect coefficients and is common to all  $m$ , and  $\boldsymbol{\gamma}_{2mijk}$  is the subject-level random-effect coefficients associated with the parameter  $\beta_m$  for the  $k^{\text{th}}$  subject within the  $j^{\text{th}}$  cluster. The random effects are assumed to follow a multivariate normal distribution with mean zero. Because the vector  $\mathbf{x}_{mijk}$  may include subject-level, cluster-level and state-level exposure variables, the fixed effects parameter vectors  $\boldsymbol{\beta}_1$  and  $\boldsymbol{\beta}_2$  represent the effects of different exposure variables on the annual changes in the pre- and post-periods. Thus, we may perform statistical tests to examine whether there are differences in trends between the pre- and post-periods overall and for each state, and whether the patterns of changes differ between the states.

Similarly for a count outcome  $Y_{ijkt}$  (e.g., number of clinical visits), we define the expected value  $\mu_{ijkt} = E(Y_{ijkt})$  and apply a Poisson regression model based on the natural log link function. The log expected number of clinical visits,  $\log(\mu_{ijkt})$ , can be modeled with the aforementioned segmented mixed-effects model. The use of an offset term in the models yields the estimates of the rate of clinical visits rather than the mean number of visits. The fixed-effect parameters,  $\beta_1$  and  $\beta_2$ , represent the effects of exposure variables on the annual changes in log of incidence rates for the pre- and post-periods, respectively. For a continuous outcome  $Y_{ijkt}$ , we will model the mean,  $\mu_{ijkt} = E(Y_{ijkt})$ , with the mixed-effects model and the parameters  $\beta_1$  and  $\beta_2$  indicate the effects of exposure variables on the annual changes in the outcomes for the pre- and post-periods, respectively. All final statistical models will be assessed with respect to the goodness-of-fit and the appropriateness of model assumptions. Statistical software SAS 9.4 and R environment will be used to implement the proposed analyses.

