*Statistical Power.* Given the very large sample sizes that are anticipated for the research studies (more than 320,000 patients with diabetes and 2,000,000 patients at-risk for diabetes), there is tremendous statistical power to detect very small effect sizes for individual-level exposure variables. Therefore, the clinical investigators on this project will need to

examine each statistically significant result and determine whether it is clinically significant. Furthermore, such large sample sizes ensure the robust estimation results from the proposed multi-level statistical modeling which involves large number of regression coefficient and covariance parameters. The major benefit of the large sample size for each research study is that it provides sufficient statistical power for investigating effects of interest within subgroups that might be constructed according to age, race-ethnicity, cohort decompositions, etc.

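### The subgroup section asks how the policy effect varies between subgroups, but the cross-subgroup analyses it commits to only average the effect and do not estimate or test variation

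*Combined protocol and SAP*

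**What the plan says.** The aim in Subgroup analyses (section 8.0) is about heterogeneity: "we will investigate subgroup analyses to assess how the policy impact varies across different subgroups". The method follows the general modelling approach, and then:

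- Each subgroup is looked at: "we will examine the benefits of policy changes for different subgroups including (1) patients with insurance throughout the study period". Groups (2) to (4) are patients who gained insurance after the policy changes, patients never insured, and patients new to the system after the changes. The fifth entry is open: "other subgroups of interest according to gender, age (e.g., age 65 and older), race-ethnicity".
- Across subgroups, the tool is meta-analysis: "We will adopt this method to evaluate the average impact of policy changes across subgroups".
- The display is cumulative: "A forest plot will be generated to reveal how the addition of a subgroup to the meta-analysis may affect the average policy impact".

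The section names no interaction term, between-subgroup contrast or heterogeneity statistic.

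Three other places in section 8.0 bear on this. The model description lets exposure variables at several levels act on the pre- and post-period slopes, and says that tests comparing states may be performed: "whether there are differences in trends between the pre- and post-periods overall and for each state, and whether the patterns of changes differ between the" (the sentence closes by naming the states). The section on population-level outcomes lets rural and urban counties follow different patterns over time. The Statistical Power paragraph says the large sample "provides sufficient statistical power for investigating effects of interest within subgroups that might be constructed according to age, race-ethnicity, cohort decompositions" and similar groupings. It also asks the clinical investigators to judge whether each statistically significant result matters clinically.

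**The concern.** A question about variation needs an estimate of a difference. An average summarises what subgroups have in common. A plot of how the average moves as subgroups are added depends on the order of entry and on subgroup size as well as on real differences. Neither gives a difference in policy effect with its uncertainty.

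That leaves the analyst with a set of within-subgroup estimates, and a Statistical Power paragraph that presents power inside subgroups as a main benefit of the sample. The natural fallback is to compare which subgroups reached significance, and that is not evidence that effects differ. Race subgroups in the diabetes cohort are very unequal in size, so where power is limited the pattern of significance can follow subgroup size. Where power is very high, every subgroup is significant and the pattern carries no information. A demographic difference in policy benefit could then be reported when there is none, or a real one could go unnoticed, in a study meant to inform future coverage policy.

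**Working it through.** The plan gives no alpha, numeric power or effect size for subgroups, so it has no figure to reproduce. The main check is a comparison of texts. The arithmetic only illustrates what could follow.

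**1. Question against method**

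| Element | Where | Addresses variation between subgroups? |
|---|---|---|
| Aim: how impact varies | Subgroup analyses | This is the question |
| General models applied to subgroups | Subgroup analyses | No contrast named |
| Meta-analysis | Subgroup analyses | Targets the average |
| Forest plot | Subgroup analyses | Shows the average shifting |
| Exposure variables on both slopes | Section 8.0, model description | Could do so, but tests are optional and name states |
| Rural and urban patterns | Population-level outcomes | Compares groups, but replaces the segmented policy model with overall trends and moves the time origin to the start of the study |

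The last row is a real between-group comparison. With the policy segments removed, however, it cannot show whether the policy effect differs.

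**2. What the existing model can deliver**

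The pre-policy slope is beta_1 and the post-policy slope is beta_2, so the policy effect on trend is beta_2 − beta_1. If a characteristic with L levels enters both x_1 and x_2, the hypothesis that beta_2 − beta_1 is the same at every level is one joint test with L − 1 degrees of freedom. Table 1 already lists age, sex, race and insurance status as individual-level exposure variables.

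**3. Pooling across the listed subgroups**

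The list mixes several ways of dividing the same patients. A woman aged 65 or older who was insured throughout falls in at least three listed subgroups (insurance, gender, age). A meta-analysis over the whole list would count her each time as if the estimates were independent.

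**4. Illustration: reading variation from within-subgroup significance**

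Inputs from the diabetes-cohort table in section 7.2: White 224,307; African-American 52,668. Assumptions: two-sided level 0.05, identical true effects, independent subgroups, standard error proportional to 1/sqrt(n).

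- Ratio of expected z values: sqrt(52,668 / 224,307) = sqrt(0.2348) = 0.485.
- Expected z in the larger group at power p_W: m = 1.96 + z(p_W). In the smaller group: 0.485 × m.
- Power at expected z of m: p = 1 − Φ(1.96 − m) + Φ(−1.96 − m).
- P(significant in White patients only) = p_W × (1 − p_A).

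| Power, White | z, White | z, African-American | Power, African-American | White only |
|---|---|---|---|---|
| 80% | 2.80 | 1.36 | 0.274 | 0.800 × 0.726 = 58% |
| 90% | 3.24 | 1.57 | 0.349 | 0.900 × 0.651 = 59% |
| 99% | 4.29 | 2.08 | 0.547 | 0.990 × 0.453 = 45% |
| 99.9% | 5.05 | 2.45 | 0.687 | 0.999 × 0.313 = 31% |
| over 99.99% | 8.00 | 3.88 | 0.972 | 1.000 × 0.028 = 2.8% |

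Under the same assumptions, a direct test of the difference at 0.05 would wrongly declare one 5% of the time in every row.

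**The case against.** The strongest reply is that the plan already contains the remedy. The subgroup section builds on the general models, those models let exposure variables act on both slopes, and Table 1 lists the relevant variables. This stands in part: the framework is adequate and the change is small. But the test language is permissive and names states, and the subgroup section then specifies an average. Nothing commits the analysis to a contrast by gender, age, race-ethnicity or insurance.

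A second reply is that the sample is very large, so discordant significance will be rare. This also stands in part. The table above shows the risk falling from 58% to under 3% as power rises. At that end, though, within-subgroup tests are uniformly significant and still say nothing about variation. The illustration also ignores the clinic and health-system random effects and the uneven site mix (African-American patients are 2% of the diabetes cohort at Utah and 36% at Temple).

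A reader might infer more than the documents support. They state no rule that variation will be judged by significance in one subgroup and not in another, and they do not say that the models will be fitted separately by subgroup. Nor does the Statistical Power paragraph invite a hunt for significant results: its instruction is to check clinical relevance, which is a caution, although it neither compares subgroups nor controls error. A reader might also see the absence of a multiplicity rule or exploratory label as the core fault. No alpha is stated for any analysis in this observational study. Family-wise error figures for the open list would rest on assumed counts, and they would measure false effects within subgroups, not false differences between them.

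**Conclusion.** The point holds in a limited form. The stated aim is to assess variation in policy impact, and the committed cross-subgroup steps do not estimate or test it. This follows from the text alone and needs no numerical assumption. A better method is available within the model already specified.

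The size of the consequence is uncertain. Under the assumptions in the working, the chance that equal effects look different by race on significance alone runs from 58% at 80% power to under 3% at an expected z of 8. This illustrates one possible misreading; it is not a prediction of what the investigators will do. Multiplicity control and an exploratory label would be sensible additions, but the conclusion does not depend on them.

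**What to change.** Revise Subgroup analyses as follows.

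- **Baseline characteristics.** Prespecify gender, age (under 65, 65 and older) and race-ethnicity, with their levels. Enter each in x_1 and x_2 of the segmented model, test jointly whether beta_2 − beta_1 differs by level, and report the difference in slope change with its 95% confidence interval.
- **Insurance groups (1) to (3).** These are mutually exclusive, so make the same contrast. Describe it as associational, because membership is partly defined by what happens after the policy.
- **Group (4).** Patients new to the system after the policy changes have no in-system pre-policy slope. Keep this group descriptive.
- **Interpretation.** Base any statement that the policy effect varies on these contrasts. Keep within-subgroup estimates and the forest plot as description.
- **Meta-analysis.** Pool only within one set of non-overlapping subgroups.
- **Optional.** Add multiplicity control across the contrasts and an exploratory label for other subgroup results.

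The cost is revised wording and some interaction terms in models already planned, with no new data. The drawback is that contrasts have less power than within-subgroup tests, so fewer differences will be claimed.

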***Diabetes Cohort Definition.*** During year 1 of the proposed project, the investigative team, in collaboration with the PaTH Network, will identify a valid cohort of patients with type 2 diabetes. The cohort of patients under study will be defined as all patients age 18 and older with an indication of type 2 diabetes during the proposed study time frame. Patients will be classified as having diabetes using a clinically validated algorithm: type 2 diabetes mellitus on the problem list, diabetes-specific medications, hemoglobin A1c (HbA1c) results > 7.0%, or one inpatient diagnosis code or two outpatient diagnosis codes for type 2 diabetes (ICD-9 codes 250.xx). The diabetes cohort will be further limited to patients who will likely be captured in the PaTH EHR records or claims data so that outcome assessments can occur. Thus, we will further limit the diabetes cohort to patients who have either: (1) had at least 2 outpatient primary care visits in one of the PaTH health systems in the past 3 years (since January 1, 2012), or (2) for whom claims data are available. The cohort will be dynamic, with new patients added into the cohort after 2015 as they meet the diabetes cohort definition prospectively. The observational period for the outcome variables will be for the 10-year period from 2009-2019, thus including 3 years of data prior to the first policy change (CMS instituting coverage for intensive behavioral therapy for obesity) and 3 years after the last policy change (Pennsylvania Medicaid expansion) under study.

Following the definition of the diabetes cohort and key diabetes outcomes and covariates as described above, an initial extraction of variables will be conducted in Year 2 of the proposed project for years 2009-2015. This early data extraction from the PaTH Network will allow for cohort validation and data cleaning and editing, as well as required programming and determination of the analysis models. We will utilize this initial data extraction in Years 2 and 3 to analyze the impact of early health policy changes, as well as to prepare a manuscript of both the protocol and early findings of policy impact. The final data extraction will occur during the final quarter of Year 4 of the proposed project, allowing for completion of a ten-year time period (2019).

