In the multi-level modeling, the first-level unit is the yearly measurement for the individual subject (pre- and post-policy), the second-level unit is the individual subject, the third-level unit is the health system or clinic within the health system (cluster), and the fourth-level unit is the state. We set year 2014 as time origin for Utah when considering the policy impact of the ACA. Let  $Y_{ijkt}$  denote the binary response of having controlled diabetes at year  $t$  since policy changes for the  $k^{\text{th}}$  subject within the  $j^{\text{th}}$  cluster of the  $i^{\text{th}}$  state,  $t = -5, -4, \dots, 0, 1, \dots, 5$ ,  $i = 1, 2, 3$ ;  $j = 1, 2, \dots, c_i$ , and  $k = 1, 2, \dots, n_{ij}$ , where  $c_i$  is the number of clusters within the  $i^{\text{th}}$  state and  $n_{ij}$  is the sample size within the  $j^{\text{th}}$  cluster of the  $i^{\text{th}}$  state. An individual subject may not be in the system for all 11 timepoints of measurement, so  $t$  will have a smaller range of values for that individual subject. Also due to the different timeline of policy changes, the number of years before and after policy changes may vary. The probability of having controlled diabetes,  $\mu_{ijkt} = E(Y_{ijkt}) = \Pr[Y_{ijkt} = 1]$ , can be described by the following segmented logistic regression model

$$\begin{aligned} \text{logit } \mu_{ijkt} &= \log \{\Pr[Y_{ijkt} = 1] / \Pr[Y_{ijkt} = 0]\} \\ &= \beta_{0ijk} + (t + 5) \beta_{1ijk} && \text{if } -5 \leq t \leq 0, \text{ pre-period before policy changes} \\ &= \beta_{0ijk} + 5 \beta_{1ijk} + t \beta_{2ijk} && \text{if } 0 \leq t \leq 5, \text{ post-period after policy changes} \end{aligned}$$

where  $\beta_{mijk}$  ( $m = 0, 1, 2$ ) are subject-specific regression parameters, with  $\beta_{0ijk}$  being the log odds of having controlled diabetes at  $t = -5$ , and  $\beta_{1ijk}$  and  $\beta_{2ijk}$  being the slopes (annual change in log odds) for the pre- and post-periods, respectively. In the framework of a mixed-effects model, each  $\beta_{mijk}$  is modeled by

$$\beta_{mijk} = \mathbf{x}_{mijk}^T \boldsymbol{\beta}_m + \mathbf{z}_{ij}^T \boldsymbol{\gamma}_{1ij} + \boldsymbol{\gamma}_{2mijk}$$

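### Insurance subgroups (1) to (3) are defined by coverage after the policy changes, so their policy effects and the pooled average are open to selection bias of unknown size and direction

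*Combined protocol and SAP*

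**What the plan says.** The Subgroup analyses part of section 8.0 states its purpose: "we will investigate subgroup analyses to assess how the policy impact varies across different subgroups". The first three groups are insurance histories: "patients with insurance throughout the study period", followed by "2) patients who obtained insurance after the policy changes, (3) patients without insurance throughout the study period". Subgroup results are then combined by meta-analysis: "We will adopt this method to evaluate the average impact of policy changes across subgroups". A forest plot is to accompany this.

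Section 7.2 says of both cohorts: "The cohort will be dynamic, with new patients added into the cohort after 2015". Section 8.0 adds: "An individual subject may not be in the system for all 11 timepoints of measurement".

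The policies under study are of two kinds. Coverage of obesity counseling (CMS in 2012, other insurers in 2013, section 2.1) changes a benefit. Pennsylvania Medicaid expansion (section 7.2) and the ACA, with 2014 as time origin for Utah (section 8.0), can change whether a patient is insured at all.

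For these subgroups the plan gives no pre-policy insurance definition, landmark date, minimum follow-up or time-varying insurance term. The propensity score analysis uses insurance coverage as an input. However, it is secondary, aims at the overall policy impact, and does not restrict coverage to pre-policy values.

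**The concern.** A subgroup meant to show who responds to a policy should be fixed before the policy acts. These three are not, for two reasons.

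- **Follow-up.** The phrase "patients with insurance throughout the study period" has two readings. If it means all years in which the patient was observed, briefly observed patients qualify easily, while a change of status needs at least two observed years. If it means all of 2009-2019, groups (1) and (3) admit only patients observed, and therefore alive and retained, for the whole window. Both readings select on follow-up, in opposite directions, and the plan does not choose.
- **The policy itself.** Gaining insurance is a possible consequence of Medicaid expansion and the ACA. Section 2.2 values Utah because it had not adopted Medicaid expansion, so the chance of entering group (2) may differ by state because of a policy under study.

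A reader of the forest plot would naturally take group (2) against group (3) as showing who benefited. Part of that contrast could come from how patients were sorted. The large sample described under Statistical Power reduces random error but not this error.

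**Working it through.** The plan gives no sample size, error rate, effect size or rate of insurance change for these subgroups, so there is no stated figure to reproduce. Every rate below is an assumption.

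**1. Counts in the documents (section 7.2 table, diabetes cohort).** Uninsured by site: 457 + 11,625 + 485 + 2,599 + 2,337 = 17,503, which matches the table and is 5.3% of 328,455. The four insurance categories sum to 128,993 + 38,730 + 125,412 + 17,503 = 310,638. That leaves 17,817 patients (5.4%) with no listed category.

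**2. Membership by years observed.** Under the observed-years reading, let h be the yearly chance that an uninsured patient gains insurance. The share still labelled never insured after k post-policy years is (1 - h)^k:

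| h | k = 1 | k = 5 |
|---|---|---|
| 5% | 95% | 77% |
| 10% | 90% | 59% |
| 20% | 80% | 33% |
| 30% | 70% | 17% |

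With h = 10% and last observed years spread evenly over 1 to 5, mean post-policy follow-up is 4.716/1.314 = 3.6 years in those who gain insurance and 10.284/3.686 = 2.8 in those who do not. (Each ratio is the sum of k times the share in the group, over the sum of the shares.)

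For any change of status at rate q per year, the chance of constant status over k observed years is (1 - q)^(k-1). With q = 10% this is 0.90 at 2 years and 0.35 at 11, a ratio of 2.6 (1.6 at q = 5%, 4.3 at q = 15%). Under the whole-window reading the direction reverses: a patient seen in only 2 years cannot enter group (1) or (3).

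**3. Effect on the estimate.** The simulation used 200,000 initially uninsured patients, t = -5 to 5, and 1 to 5 post-policy years each. Patient intercepts had SD 1. Yearly residuals had SD 1 and lag-one correlation 0.5. Pre-policy slopes had SD 0.05. The true mean slope change was 0. The log-odds of gaining insurance each year started at 10% odds-equivalent, log(0.1/0.9), and rose by d per unit of the current outcome. The segmented model of section 8.0 was fitted as a linear model with patient fixed effects, separately by group. Estimated slope change per year:

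| d | SD of post-policy slopes | All patients | Gained insurance | Never insured |
|---|---|---|---|---|
| 0 | 0.1 | 0.000 | 0.000 | 0.000 |
| 0 | 0.2 | +0.001 | -0.001 | +0.001 |
| 0 | 0.3 | -0.001 | -0.004 | 0.000 |
| 0.5 | 0.1 | +0.002 | +0.004 | -0.014 |
| 0.5 | 0.2 | +0.002 | +0.030 | -0.032 |
| 0.5 | 0.3 | -0.001 | +0.067 | -0.063 |
| 1.0 | 0.1 | -0.002 | -0.001 | -0.029 |
| 1.0 | 0.2 | +0.001 | +0.036 | -0.056 |
| 1.0 | 0.3 | -0.002 | +0.087 | -0.109 |

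In a variant where post-policy slopes did not vary and gain depended only on the yearly residual (d from 0.25 to 1.0), both groups shifted by -0.003 to -0.016, and the difference between them stayed within 0.004.

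Unequal follow-up alone (d = 0) gave essentially no false change. The distortion appeared when gain tracked the outcome, and it grew with variation in post-policy slopes. All initially uninsured patients, taken as one group fixed before the policy, gave about 0 in every case. The signs follow from the assumed direction of dependence. The simulation covers groups (2) and (3) only.

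**The case against.** Several counter-arguments have weight.

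- **Are the effects shown to be biased?** A reader might infer that they are, or that differences between the groups cannot be effect modification. The documents support neither. The false change vanishes if insurance gain is unrelated to the outcome, and real effect modification is not excluded.
- **Does the 2.6-fold ratio measure the harm?** No. It describes entry into groups under an assumed switching rate and one reading of the wording. One rate for everyone is also crude in a cohort where 38% are on Medicare and 5% are uninsured.
- **The planned model tolerates incomplete series.** Section 8.0 expects patients with fewer than 11 points. This stands for unequal follow-up alone. It does not cover sorting patients by a later event related to the outcome.
- **Patients who lose insurance.** One might infer that they are excluded. The list of subgroups is introduced as illustrative and ends with an open category, so the text does not say that.
- **Policy dependence is uneven.** Counseling coverage does not itself confer insurance. The argument that the policy changes membership applies to Medicaid expansion and the ACA.
- **Scope.** The primary individual-level model uses all patients and is untouched.

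What remains is that the labels need post-policy data, the plan attaches policy effects to them and pools the results, and nothing elsewhere repairs this.

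**Conclusion.** The point holds in a bounded form. Insurance subgroups (1) to (3) are defined after the policies. On either reading of the wording, membership depends on observation time, and for Medicaid expansion and the ACA it may depend on the policy. The subgroup policy effects, and the average and forest plot built on them, are open to selection bias whenever insurance gain or follow-up is related to the course of the outcome. The plan gives no reason to assume that it is not.

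Size and direction are unknown. The simulated range, from about 0 to +0.09 and -0.11 per year, shows that the mechanism can matter. It is not a forecast for this study. The change is worth making before the subgroup analyses are run; it does not call the main analysis into question.

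**What to change.** For policy-effect estimates, define insurance subgroups by status in the last year before the relevant policy: insured, by payer, versus uninsured, with a category for unknown status. Name that year for each policy and state, because there is no single date: section 2.1 gives 2012 and 2013, section 8.0 gives 2014 for Utah, and section 7.2 places Pennsylvania Medicaid expansion last.

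Analyze patients first seen later apart, by status at entry. They have no pre-policy years of their own from which to estimate a change in slope. Keep the insured-throughout, gained-insurance and uninsured-throughout groups as description only, outside the pooled average, and state which reading of the study period applies to them.

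The cost is mainly wording in section 8.0, and the gained-insurance group loses its policy-effect estimate. The fix relies on insurance status being recorded by year. Table 1 in section 7.2 lists insurance status without saying so, and this should be confirmed with the sites. Some selection on later observation will remain, because eligibility rests on visits since January 1, 2012 or on available claims.
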